6.1 Definitions

Adverse Event (AE): Any untoward medical occurrence in a patient or clinical study

subject.

Serious Adverse Event (SAE): Any untoward and unexpected medical occurrence or effect that:

- **Results in death**
- **Is life-threatening** – refers to an event in which the subject was at risk of death at the time of the event; it does not refer to an event which hypothetically might have caused death if it were more severe
- **Requires hospitalisation, or prolongation of existing inpatients' hospitalisation**
- **Results in persistent or significant disability or incapacity**
- **Is a congenital anomaly or birth defect**

6.2 Adverse events

There are no risks to the patients or the fetus from this study. There is also no evidence to suggest any harm to the mother or the pregnancy associated with the use of ultrasound. Patients may experience slight discomfort when the probe is placed, though this is usually considered less than the discomfort experienced with vaginal examinations. We will be using probe covers and disinfection spray to clean the probe between patients. Medical judgement will be exercised in deciding whether an AE is serious in other situations. Important AEs that are not immediately life-threatening or do not result in death or hospitalisation but may jeopardise the subject or may require intervention to prevent one of the other outcomes listed in the definition above, will also be considered serious.

6.3 Reporting procedures

All adverse events will be reported. Depending on the nature of the event the reporting procedures below will be followed. Any questions concerning adverse event reporting will be directed to the Chief Investigator in the first instance.

Non serious AEs

All such events, whether expected or not, will be recorded.

Serious AEs

An SAE form will be completed and faxed to the Chief Investigator within 24 hours. However, relapse and death and hospitalisations for elective treatment of a pre-existing condition do not need reporting as SAEs.

All SAEs will be reported to the Chief Investigator who will determine if the event was:

- **Related-** resulted from the administration of any of the research procedures; and
- **Unexpected-** an event that is not listed in the protocol as an expected occurrence
- **Unrelated-** an event that is not related to the study

Reports of related and unexpected SAEs will be submitted within 15 days of the Chief Investigator becoming aware of the event, using the NRES SAE form for non-IMP studies. The Chief Investigator will also notify the Sponsor of all SAEs.

Local investigators will report any SAEs as required by their Local Research Ethics Committee, Sponsor and/or Research & Development Office.

Contact details for reporting adverse events:

Chief Investigator:

[name] MD MRCOG

Consultant in Obstetrics and Feto-maternal Medicine

Centre for Fetal Care, Queen Charlotte's & Chelsea Hospital

[name]

E-mail: [contact]

[contact]

7. Study Population and Sample size

Recruitment will start upon approval of the study. The infrastructure, research fellow, ultrasound machines, and the database are already in place, which ensure that the study can start promptly upon approval, without affecting or compromising routine clinical service provision.

We aim to recruit minimum number in the groups according to the following calculations²⁹:

Primary outcome:

Acceptability

In studies thus far, acceptability of transperineal ultrasound (with no or minimal pain) varies from 68%³⁰ to 95%³¹ compared with 20% for vaginal examinations³⁰. Using the lowest percentage of acceptability at 68%, with an alpha of 0.05 and a power of 90%, the minimum sample size required is 42 patients. However, given that this area has been poorly researched before and the power calculation is purely indicative, we would expect to collect at least 100 questionnaires.

Feasibility

A recent study by our group has shown that 95%¹⁵ of transperineal ultrasound parameters can be obtained compared to 82% of digital vaginal examination parameters¹⁵. With an alpha of 0.05 and a power of 90%, the minimum sample size required is 250 patients.

Labour prediction model

For the labour prediction model, there are approximately 15 variables with 10 patients needed per variable³²⁻³⁴ and an approximate 25% Caesarean section rate^{28,35,36} (the primary outcome) in the UK currently. This equates to 600 patients needed for the study.

Calculation:

$$15 \times 10 \times (100/25) = 600 \text{ patients}$$

As already discussed above, for statistical power and significance, a minimum of 42 and 250 patients is required for acceptability and feasibility respectively (24-42 weeks). For the predictive modelling, 600 patients are required (37-42 weeks).

The majority of the patients for the acceptability and feasibility samples will be recruited from the predictive modelling group (gestation 37-42 weeks). However, to allow sufficient data collection for feasibility, acceptability and development of the model, at least 700 patients will be required. As the trust has an annual delivery rate of 9000 annually, over a 24-month data collection period with a delivery rate of 18,000 across the trust, 700 patients (4%) sample size is achievable.

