2.2 Study Rationale and Hypothesis

Several studies have assessed the accuracy of transabdominal ultrasound in comparison with digital VE in determining fetal head position¹⁸⁻²¹. These have concluded that digital VE fails to identify the correct fetal head position in the majority of cases, especially at cervical dilatation $\leq 3-4\text{cm}$. Although transperineal ultrasound has been used pre-labour to predict the likelihood of PPROM patients going into labour²², its feasibility has not yet been assessed in the investigation and management of women either presenting with or established in labour. Initial studies have assessed head descent¹² and rotation²³ and angle of progression in labour^{13,24} to assess the second stage of labour to predict the likelihood of spontaneous vaginal delivery, instrumental delivery or Caesarean section. However, there have not been any studies directly assessing the feasibility of transperineal ultrasound scans.

We hypothesise that transperineal ultrasound will be a feasible and acceptable technique in comparison with digital vaginal examinations for 24-42 weeks gestation.

Using the data gathered in term patients, we will develop a model to predict pregnancy outcomes. This may aid in delivery of care to pregnant women by providing a real-time online calculation tool for the likelihood of vaginal delivery and length of labour based on repeat ultrasound measurements. This will allow a more

accurate prediction of the mode of delivery and reduce the number of vaginal examinations. This will improve the information available to women and their birth partners about the progress of their labour.

We anticipate improvements to women's health with additional information allowing better decision-making during labour enhancing the accurate recording of labour to a recordable skill. Universally, it may reduce the frequency of intrusive internal examinations and associated infection and will also be potentially useful in allowing the assessment of women in whom digital VE is traumatic or contra-indicated.

Overall, it may create a paradigm shift on delivery units in an area where the standard assessments have not changed in over one hundred years allowing better provision of resources.

3. Study Objectives

Primary objectives:

1. Feasibility of transperineal ultrasound scanning
2. Acceptability of transperineal ultrasound scanning
3. Creation of a "Sonopartogram" (Figure 3); an ultrasound based labour record

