4.5 Exclusion Criteria

- Younger than 18 years.
- Imminent iatrogenic intention to deliver
- Life threatening maternal or fetal compromise needing immediate medical attention and/or delivery
- Women who in the opinion of the researcher by virtue of language or learning impairment would be unable to give fully informed consent to the study.
- Miscarriage
- Intra-uterine death
- Previous cervical surgery eg. cone biopsy, cervical cerclage. Note- Single LLETZ is not excluded.
- Non-cephalic presentations
- Multiple pregnancies (for the term predictive model group)
- Multiparous patients (for the term predictive model group)
- Not in established labour (for the term predictive model group)

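### Feasibility and acceptability are claimed for 24-42 weeks, but most of the sample is to come from nulliparous women in established term labour, with no preterm minimum and no estimate by gestation

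*Combined protocol and SAP*

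**What the plan says.** **The claim.** Section 2.2 hypothesises that transperineal ultrasound will be "a feasible and acceptable technique in comparison with digital vaginal examinations for 24-42 weeks gestation". The first null hypothesis in the Study Summary covers the same range.

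**The minima.** Section 7 attaches both to the whole range: "a minimum of 42 and 250 patients is required for acceptability and feasibility respectively (24-42 weeks"). It expects at least 100 questionnaires, requires 600 women for the term model, and sets the overall figure in these words: "feasibility, acceptability and development of the model, at least 700 patients will be required".

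**The source of the women.** Section 7 also states: "The majority of the patients for the acceptability and feasibility samples will be recruited from the predictive modelling group". The Study Summary and section 7 place that group at 37-42 weeks. Sections 4.4 and 4.5 exclude from it multiparous women, multiple pregnancies and women not in established labour.

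**The analysis.** Section 7.1 has one block for acceptability and feasibility, headed 24-42 weeks, and a general significance threshold of p<0.05. It names no estimate by gestation, parity or labour status.

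**The questionnaires.** Section 4.9 gives the pre-study and post-study questionnaires to the acceptability and feasibility group and says that the model group has no additional ones.

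**The concern.** The claim is wider than the evidence the plan secures. A woman at 28 weeks who is not in labour and a nulliparous woman in active labour at term plausibly differ in how readily cervix and head can be assessed by either method, and in how uncomfortable each examination is. The protocol itself recognises some of this: section 2.2 reports that digital examination misjudges head position particularly at low dilatation.

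If one overall estimate is reported and most of its women are in term labour, that estimate mainly describes term labour. A favourable result would still answer the hypothesis as worded and be read as applying from 24 weeks. The women least represented include some of those who motivate the study, such as women with preterm prelabour rupture of membranes, named in section 2.1 as a setting where digital examination is contraindicated.

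**Working it through.** **1. The plan's own figures reproduce.** Section 7 gives alpha 0.05 and power 90%, but no formula or sidedness. For two independent proportions (two-sided, pooled variance under the null, no continuity correction):

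n per technique = [1.960·√(2·p̄(1−p̄)) + 1.282·√(p1(1−p1) + p2(1−p2))]² / (p1−p2)²

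- Feasibility, 95% v 82%, p̄ = 0.885: 124.5, so 125 per technique and 250 in total.
- Acceptability, 68% v 20%, p̄ = 0.44: 20.3, so 21 per technique and 42 in total.
- Model: 15 × 10 × (100/25) = 600.

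The arithmetic is not at fault. The question is who the women are.

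**2. Composition.** Suppose recruitment stops at the two minima.
- Outside the model group: 700 − 600 = 100 women.
- As a share of a 250-woman feasibility sample: at most 100/250 = 40%. This fits the statement that the majority come from the model group.
- These 100 could be multiparous women at term, women at term not in established labour, or women at 24-36 weeks. No split is stated.
- Smallest preterm number that meets every stated minimum: 0.

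**3. Precision in a preterm stratum.** Assume, for illustration only, that 33 of the 100 are preterm. The Wilson 95% interval is (p + z²/2n)/(1 + z²/n) ± z·√(p(1−p)/n + z²/4n²)/(1 + z²/n).
- Feasibility, 31/33 = 93.9%: 0.894 ± 0.090, or 80.4% to 98.3%. This includes the 82% given for digital examination.
- Acceptability, 22/33 = 66.7%: 0.649 ± 0.153, or 49.6% to 80.2%. This is far above the 20% given for vaginal examination.

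**4. Power in a preterm stratum** (unpaired, two-sided, section 7's rates, n per technique):

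| Preterm n | 95% v 82% | 68% v 20% |
|---|---|---|
| 20 | 25% | 90% |
| 33 | 38% | 99% |
| 50 | 53% | >99% |
| 100 | 83% | >99% |
| 125 | 90% | >99% |

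The shortfall is mainly in feasibility. Each woman may have both examinations, so a paired analysis is natural. Its power depends on a within-woman correlation that the documents do not give.

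**5. Could an overall result hide a poor preterm one?** Assume 10% preterm with 70% of parameters obtained by ultrasound, 95% obtained at term, and 82% by digital examination throughout. The overall ultrasound rate is 0.9 × 95% + 0.1 × 70% = 92.5%. Against 82%, power to favour ultrasound is about 70% with 125 per technique and 94% with 250 per technique, although in the preterm women ultrasound does worse than digital examination. These inputs are assumptions; the example shows only that masking is possible.

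**6. Related wording.** Feasibility measure (b) in section 7.1 counts only occasions when a digital examination was intended. Section 4.9 compares women in whom it is contraindicated with speculum findings, so as worded they fall outside that measure.

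**The case against.** Preterm women are not excluded. Section 4.4 admits women from 24 weeks, section 4.7 recruits in the Fetal Medicine Unit, Day Assessment Unit and Maternity Triage, and section 4.9 provides for a speculum comparison. Some preterm women will probably be enrolled, so a reader who infers that the study cannot include them goes too far. What stands is that no number is assured and no separate estimate is planned.

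A reader might also compute 100/700 = 14% and call it the ceiling on women outside term labour. The documents do not support that. Both 600 and 700 are floors, section 7 gives no formula for 700, and the relevant denominators are the samples of 250 and of 42 or about 100 questionnaires.

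Nor is it settled that term labour dominates the acceptability sample. Section 4.9 gives the model group no additional questionnaires. Read literally, questionnaires come from outside that group unless women join both studies, and section 7 says the opposite.

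Pooling is inferred from a single heading and the absence of any stratified analysis; section 7.1 does not use the word. For acceptability it names a Likert questionnaire but no test. The design overview and flowchart are not visible in the text available, so an allocation by gestation shown there cannot be ruled out.

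Finally, section 7 calls the acceptability calculation only indicative, and that contrast is so large that about 20 preterm women could show it. This objection holds for acceptability. It does not help feasibility.

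**Conclusion.** The concern holds as a mismatch between the stated claim and the evidence the plan secures. As written, a result from mostly nulliparous women in established term labour could be reported as feasibility and acceptability from 24 weeks, and a sample with no preterm women would satisfy every stated minimum. The consequence falls mainly on feasibility: with 33 preterm women (assumed), the interval of 80-98% would not separate ultrasound from the 82% quoted for digital examination, and power would be about 38%.

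This rests on reading section 7.1 as one overall analysis and on recruitment at the stated minima. It does not show that preterm women will be absent, that their results will be worse, or that the findings for term labour are unsound. The change is worth making because it costs little; the study does not fail without it.

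**What to change.** - In section 7.1, pre-specify feasibility and acceptability estimates with 95% confidence intervals for three strata: 24-36 weeks, term not in established labour, and term in established labour. Report the number of women in each.
- In the hypothesis and the conclusions, limit the 24-42 week statement to strata actually populated, and describe sparse strata by their intervals rather than by an overall p-value.
- Reconcile section 4.9 (no additional questionnaires in the model group) with section 7 (most of the acceptability sample drawn from that group), stating whether women may join both studies and who completes the questionnaires.

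**Cost.** Changes to analysis and wording only. Gestation is already in the section 4.9 dataset, and established labour is already judged by the attending clinician for entry to the model group. No extra women, visits or recruitment quota are needed. The drawback is that the claim for preterm women may become narrower: separate reporting shows how much preterm evidence there is, but does not guarantee any.

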7.1 Statistical and Data Analysis

In both groups, data will be collected prospectively and compared with vaginal examinations. In the second group, there will also be additional longitudinal measurements.

We will use a p value of <0.05 to indicate significance.

All measurements will be entered online at the time of examination to a secure database on the Imperial College Healthcare NHS Trust shared server where the patient will be identified by study number only. The database entry page will be accessible to investigators on their login, though they cannot interrogate data already entered. The data rules will follow closely to those performed through the recently completed multicentre European TRUFFLE study of fetal growth restriction where ultrasound measurements were captured at the time of examination³⁷.

For 24-42 weeks assessment of acceptability and feasibility:

Acceptability and preference will be tested using a questionnaire with Likert scale for discomfort, adapted from the W-DEQ Score³⁸

Feasibility of the ultrasound technique will be compared to digital VE for (a) total number of observations missing (head descent, position and cervical dilatation) during an admission on the delivery unit and (b) number of ultrasound examinations or digital VEs that could not be carried out for whatever reason where there was an intention to carry out a digital VE.

As a part of feasibility, *Reproducibility* between the *ultrasound and digital VE techniques* will be assessed both as a correlation (r) and agreement (using the Bland Altman method) between the ultrasound method and digital VE for head descent and cervical dilatation, and the Kappa statistic for head position.

Term predictive model:

The predictive value of intrapartum ultrasound parameters will be investigated using linear and logistic regression analyses. We will calculate the Receiver Operating Characteristic (ROC) curve with the Area Under the Curve (AUC) and associated positive and negative predictive values for delivery outcomes in the evaluation of transperineal ultrasound as a diagnostic tool.

8. Study supervision and Monitoring

Central and local supervision: the chief principal investigator at Imperial College London will be responsible for the protocol, quality control, interim analyses of the data, advice on progress and final analysis and reporting of the study. The Imperial Joint Research Compliance Office may audit the study as part of routine research governance.

9. Regulatory Issues

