4.7 Recruitment methods

All groups will be identified by the project manager and emphasis will be placed on recruiting patients antenatally as much as possible. The project manager is a member of the participants care team. The project manager will organise the recruitment and written consent, which can be obtained by any one of the research team members that will have been trained (expected to be up to 8 doctors and midwives on the delivery units of both QCCH and SMH although primarily it will be at QCCH). These doctors and midwives will undergo induction and then maintenance training in the study protocol, transperineal ultrasound and data entry/governance

including GCP training. Where a midwife performs the ultrasound examination, it will not be the same midwife responsible for the ongoing care and digital VEs of that woman: another midwife or doctor should perform the examination. Where a doctor performs the ultrasound examination, that doctor will not make the decision for a course of action, it will normally be made by the next most senior doctor. Ultrasound examinations should not be the basis for a course of action unless a clinically unexpected and important situation that would change clinical management is not disclosed through digital VE but is through ultrasound.

Ahead of recruitment, a press release on the Imperial College Healthcare NHS Trust and Imperial College website will display recruitment posters. We will advertise on other relevant websites and display recruitment posters at other sites.

Recruitment areas

- Patient's attending the Early Pregnancy Unit (≤ 20 weeks gestation)
- Antenatal Clinic (all trimesters)
- Parent Craft classes (second and third trimester)
- Fetal Medicine Unit (all trimesters)
- Day Assessment Unit, Maternity Triage and Labour Ward (≥ 20 weeks gestation).

The project manager will organise a formal meeting with the charge nurses from all areas to inform them of the study upon ethics approval.

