Transperineal ultrasound will then be carried out between gestations 24-42 weeks when a vaginal or speculum examination is otherwise also required to assess acceptability and feasibility. This scan will be done either immediately before or after the digital vaginal examination and the timing in relation the digital vaginal examination will be recorded.

Predictive Model:

In the predictive model group, there are no additional questionnaires. An admission ultrasound scan will be performed when the patient is deemed to be in established labour by the attending clinician. Subsequent scans will be performed as required at the time of routine clinical examinations typically between 2-4 hours apart.

The admission ultrasound scan will include if feasible fetal Doppler assessment of the umbilical artery, the cerebro-umbilical ratio (C/U: MCA/PI)¹⁶. Amniotic fluid index will also be measured. Fetal position will be assessed with a transabdominal scan and recorded as described above.

Dataset

Fixed variables

Maternal

Gestation

BMI, Age²⁸, Parity, Height, Ethnicity

Contraindication to vaginal examinations

Reason for avoidance of vaginal examinations

Fetal

EFW if known

Singleton

Multiple

Intrapartum

Non-USS:

Rupture of Membranes Yes/No: If Yes: Time

Spontaneous onset of labour Yes/No: If Yes: Time

Induction of Labour with prostaglandins Yes/No: If Yes: Time at insertion of prostaglandin

Syntocinon Yes/No: If Yes: Time
Epidural analgesia Yes/No: If Yes: Time

Modifiable parameters

USS Parameters: modified as labour progresses

- head position (TA ultrasound scan)
- cervical dilatation
- head-perineum distance
- caput
- moulding

Prolonged first stage of labour will be diagnosed according to national guidelines set in the UK by the National Institute of Health and Clinical Excellence (NICE) guidelines (cervical dilatation of < 2 cm in 4 hours)²⁵.

If recruited to the study, all patients will undergo normal clinical management with digital VEs or speculum examination performed as planned and in addition, ultrasound examinations before the digital VE/speculum by trained professionals. These ultrasound examinations will be blinded to the normal caregivers (midwives or doctors) so that they do not influence clinical management, though for practical reasons it will not be possible to blind the ultrasound operator to the clinical findings.

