In women where **digital** vaginal examinations are contraindicated, we will compare ultrasound observations to those obtained by speculum. In all other women, ultrasound measurements will be compared to the corresponding digital vaginal examinations. In women who decline **digital** vaginal examinations for psychological reasons, this will be noted.

There are no additional visits outside the normal care pathway for the patient. The length of years of obstetric experience of the healthcare professional carrying out the digital vaginal examinations, speculums, ultrasound scan and the delivery will be recorded.

Study Timeline

The study will run according to the following timeline:

- **Months 0-3:** Ethics completion, staff training, and setting up web based study screens
- **Months 3-27:** Active study recruitment
- **Months 27-36:** Analyses and write up of an ultrasound based labour record (the sonopartogram) and development of a predictive model.

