4.14 External peer review

An earlier version of this protocol has been subject to external peer review by the British Medical Association leading to external funding (Helen Lawson Grant, awarded July 2014)

5. Study Outcome Measures

5.1 Primary measures:

1. Assessing feasibility of ultrasound by comparison with digital vaginal examinations:

- *Digital vaginal examination*: cervical dilatation, head station, caput, moulding, head position
- *Ultrasound*:
 - *Transabdominal Ultrasound*: Fetal head position
 - *Transperineal Ultrasound*: Cervical dilatation, head-perineum distance, caput and moulding

2. Acceptability of Transperineal Ultrasound to patients

3. Dataset for predictive model of outcome of labour of Caesarean section due to failure to progress and/or fetal distress

- Time to delivery

- Mode of delivery
- Primary indication for delivery
 - failure to progress
 - suspected fetal compromise

5.2 Secondary measures:

1. Neonatal outcome

- Gender
- Birth-weight
- Apgar Scores at 1 and 5 minutes
- Cord Gases
 - Fetal acidosis defined as arterial pH <7.10 and base excess >12.0mmol/l
- Neonatal unit admission within 24 hours
- Neonatal morbidity

6. Adverse events and reporting procedure

RISK ASSESSMENT - This study will not involve any risk to the participants. There are no predicted risks associated with the additional transabdominal and transperineal ultrasound scan. The scans will be used at the same settings and duration as routine ultrasound. We will be using probe covers and disinfection spray to clean the probe between patients.

The patient will be managed accordingly in concordance with local guidance and follow up arrangements will be made. The patient will still be followed up for the purposes of the study.

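### Feasibility count (b) pools every missed scan or digital VE whatever the cause, and the dataset lists no reason for a missed scan

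*Combined protocol and SAP*

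**What the plan says.** Feasibility is the first primary measure in section 5.1: "Assessing feasibility of ultrasound by comparison with digital vaginal examinations". Section 7.1 gives it two counts.

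- Count (a) is the "total number of observations missing (head descent, position and cervical dilatation) during an admission on the delivery unit".
- Count (b) is the "number of ultrasound examinations or digital VEs that could not be carried out for whatever reason", limited to occasions "where there was an intention to carry out a digital VE".

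Section 7.1 does not split (b) by cause and does not define intention.

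Other sections bear on how an examination comes to be missed:

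- **Scan operators.** Section 4.7 describes the trained team as "expected to be up to 8 doctors and midwives on the delivery units of both QCCH and SMH". A midwife who scans may not be the one giving that woman's care and VEs. Under section 4.9, the scan in the acceptability and feasibility group is done immediately before or after the VE.
- **Refusal of VE.** Section 4.9 says of women who decline digital "vaginal examinations for psychological reasons, this will be noted". It gives no rule for the analysis.
- **Recorded reasons.** The dataset in section 4.9 includes "Reason for avoidance of vaginal examinations" and contraindications to VE. It lists no equivalent item for a scan that was not done.

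**The concern.** The two methods do not reach a missed examination by the same routes. Every participant has consented to a study of perineal scanning, so women unwilling to be scanned are partly filtered out before counting begins. A VE that was intended and then refused is charged to VE. In the other direction, the VE is done by whoever is giving care, while the scan needs a second, trained person at the right moment. Count (b) is triggered by an intention to do a VE, so a scan missed because no operator was free is charged to ultrasound.

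These losses pull the comparison in opposite directions, and neither shows whether the technique works when it is tried. With one all-cause total and no scan-side reason, the analysis cannot tell a technical difference from refusal or research staffing. Refusal also belongs partly to acceptability, the second primary measure, so pooling blurs the two.

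**Working it through.** **Step 1: the plan's own figure.** Section 7 assumes 95% of ultrasound parameters and 82% of VE parameters are obtained, with alpha 0.05 and power 90%, and states 250 patients. Sidedness is not stated; two-sided is assumed here. The pooled two-proportion formula is

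n per group = [1.960 × √(2 × 0.885 × 0.115) + 1.2816 × √(0.95 × 0.05 + 0.82 × 0.18)]² / 0.13²

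= (0.884 + 0.566)² / 0.0169 ≈ 124.5, rounded up to 125, or 250 in total.

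The figure reproduces. It rests on parameters obtained, which is closer to count (a) than to (b), so it is not in question here.

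**Step 2: a model for count (b).** The documents give no rate of examinations carried out, no refusal rate and no operator-absence rate. For illustration, 95% and 82% are borrowed as success when attempted. Let r be the share of intended VEs refused and o the share of occasions with no scan operator, acting independently of technical failure:

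- ultrasound carried out = 0.95 × (1 − o)
- VE carried out = 0.82 × (1 − r)

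| r (assumed) | o (assumed) | Ultrasound | VE | Ultrasound minus VE |
|---|---|---|---|---|
| 0 | 0 | 0.950 | 0.820 | +13.0 points |
| 5% | 0 | 0.950 | 0.779 | +17.1 |
| 10% | 0 | 0.950 | 0.738 | +21.2 |
| 0 | 10% | 0.855 | 0.820 | +3.5 |
| 0 | 20% | 0.760 | 0.820 | −6.0 |
| 5% | 20% | 0.760 | 0.779 | −1.9 |
| 10% | 20% | 0.760 | 0.738 | +2.2 |

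**Step 3: thresholds.**

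- With no refusals, the sign reverses when 0.95 × (1 − o) < 0.82, that is o > 1 − 0.82/0.95 = 13.7%.
- VE refusal cannot reverse the sign at 95% v 82%; it only widens the gap. It could hide an ultrasound disadvantage if there were one. At 90% v 95%, r above 1 − 0.90/0.95 = 5.3% would do so. At 95% v 98%, r above 1 − 0.95/0.98 = 3.1% would.
- If both techniques succeeded 95% of the time, a 5% refusal of VE alone would give ultrasound an apparent advantage of 0.95 − 0.95 × 0.95 = 4.75 points. A 5% operator absence alone would give VE the same advantage.

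**The case against.** An all-cause count is a legitimate pragmatic measure. On a delivery unit, refusal and the lack of a trained operator are part of whether a method can be used. Section 2.2 also presents ultrasound as potentially useful where VE is traumatic or contraindicated, so setting refused VEs aside would discard part of the rationale. This stands, and it is why the all-cause count should stay. Analysing only occasions when both methods were attempted would change the question and bring its own selection.

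The illustration is weak as a forecast. The 95% and 82% are shares of parameters, and a VE that was done but missed one parameter is not a failure under (b). The loss rates are assumed. Section 4.1 also lets other suitably trained staff contribute data by agreement, so the team of 8 is an expectation and not a ceiling. This stands too: the figures show direction and sensitivity only.

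The intention clause narrows (b). Section 2.1 says VE is usually avoided in advance for women with fear of childbirth, previous sexual trauma or vaginismus, and section 4.9 substitutes speculum findings where VE is contraindicated. Both groups arguably fall outside (b). But a refusal after a VE was intended still counts, and the clause does nothing about scans missed for want of an operator.

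Reasons are partly captured on the VE side, and the data-entry screens are not among the documents, so a scan-side field may exist. The documents do not show one, and section 7.1 plans no use of it.

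Count (a) might seem a safeguard. On a plain reading, though, an examination not done leaves its observations missing, so (a) may carry the same mixture.

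**Conclusion.** The point holds as a cheap improvement to the plan. As written, count (b) cannot separate technical failure from refusal or research staffing, and the listed dataset lacks the scan-side reason needed to do so. Under the assumed loss rates, the ultrasound advantage could lie anywhere from about 21 points to −6 points with no change in how either technique performs. That range depends on the borrowed 95% and 82%, on independence of the causes, and on refusal and absence rates the documents do not give.

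Four stronger readings are not supported:

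- **VE refusals could reverse the result.** At the protocol's percentages they widen the gap in favour of ultrasound. Reversal needs operator absence above about 13.7%.
- **Refusals fall almost entirely on VE.** This is a plausible inference from the consent process, but no figure supports it. A consented woman may still decline a scan, and sections 4.6 and 9.2 leave withdrawal open at any time.
- **Count (b) is the primary feasibility comparison.** It is one of two counts, and the sample size is not built on it.
- **The all-cause count is an error to be replaced.** It is a defensible measure that needs a breakdown.

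**What to change.** 1. Keep the all-cause count (b).
2. State in section 7.1 when a VE counts as intended, including how a VE declined in advance is treated.
3. Record one reason code for every scan or VE not carried out, with the same list for both methods: declined by the woman; stopped by the woman; no trained operator or no time; attempted but not obtained; other.
4. Report (b) split by reason for both methods, beside the total.
5. State that operator unavailability will not be attributed to the technique when concluding on feasibility.
6. If wanted, add an analysis of occasions when both methods were attempted, as supportive only.

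The cost is one coded field on the online entry page, a few sentences in section 7.1, and several figures in place of one. The field should be in place before recruitment, because reasons not recorded at the time may not be recoverable.
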